Pain, Enjoyment of Life, and General Activity (PEG) and Patient Global Impressions Scale (PGIC) will be assessed at 6 weeks (midpoint of intervention period one), 12 weeks (Visit 1), 18 weeks (midpoint of intervention period two), 24 weeks (Visit 2), and 36 weeks post-baseline (12 weeks after intervention period two). Basic safety assessments will also be performed at these time points to assess participant tolerability to their current study intervention(s). Patients who are unable to tolerate their assigned study treatment will be educated on how to safely discontinue their current treatment plan but will otherwise remain in the study.

Objectives:

The primary objective is to estimate an algorithm to assign sequences of two cLBP treatments based on phenotypic markers and an individual patient's response to the initial treatment (*i.e.*, a dynamic treatment regime (DTR)) that optimizes effectiveness. as characterized by the primary and secondary endpoints.

The study has the following three secondary objectives:

- Estimate DTRs that optimally balance multiple outcomes, taking into account participant preferences for outcomes including pain intensity, pain interference, physical function, opioid use, depression, anxiety, sleep duration and sleep disturbance.
- Estimate DTRs that incorporate additional phenotypic markers (i.e., deep phenotyping) collected on a subset of participants.
- Assess whether effectiveness is sustained on outcomes collected
 24 weeks after randomization to the second treatment.

Analyses for secondary objectives will utilize the set of primary and secondary endpoints.

The study has the following exploratory objectives:

- Evaluate the comparative effectiveness of individual treatments.
- Evaluate the comparative effectiveness of different treatment regimes (i.e., a particular regime with a given set of rules at each decision point).
- Evaluate the impact of treatment order on outcomes.

Analyses for exploratory objectives will utilize the set of primary and secondary endpoints.

The primary endpoint for the study is 24-week change from baseline in patient-reported pain intensity and interference, measured with the Pain, Enjoyment of Life, and General Activity (PEG) scale.

Secondary endpoints are:

- 24-week change from baseline in pain interference, measured with the 4-item PROMIS Pain Interference scale (PROMIS-PI, 4a)
- Incidence of any opioid use at 24 weeks post baseline.

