12. STUDY ASSESSMENTS AND PROCEDURES

12.1. EFFICACY ASSESSMENTS

Study outcomes will be assessed by self-report using a series of validated instruments to measure pain intensity and interference, physical function, depression, anxiety, sleep disturbance and duration, and opioid use. Patient-reported outcome measures will be administered at study baseline as well as at 12-and 24-weeks following first-stage randomization using a web-based survey platform. The primary endpoint is based on the Pain, Enjoyment of Life, and General Activity (PEG) scale, a 3-item assessment of pain intensity and interference with enjoyment of life and general activity over the past week. Response values for each item range from 0 to 10 and the average score across the three items will be used as the outcome value.

Secondary outcome assessments include:

- PROMIS Pain interference scale (PROMIS-PI, 4a)
- Current use of opioid medication on a daily basis
- PROMIS Physical Function (PROMIS-PF Short Form 6b)
- PROMIS 4-item Depression scale (from the PROMIS 29 profile)
- PROMIS Emotional Distress-Anxiety scale (PROMIS-EDA 4a)

- PROMIS Sleep disturbance (PROMIS short form 6a)
- Sleep duration (reported number of minutes asleep per night over the past month)

Primary and secondary endpoints

- Primary endpoint: 24-week change from baseline in patient-reported pain intensity and interference, measured with the Pain, Enjoyment of Life, and General Activity (PEG) scale at Visits 0 (baseline) and 2 (24 weeks of treatment)
- **24-week change from baseline in pain interference**, measured with the 4-item PROMIS Pain Interference scale (PROMIS-PI, 4a) at Visits 0 (baseline) and 2 (24 weeks of treatment)
- Incidence of opioid use, measured by self-report at Visit 2 (24 weeks of treatment)
- **24-week change from baseline in physical function**, measured with the PROMIS-PF Short Form 6b at Visits 0 (baseline) and 2 (24 weeks of treatment)
- **24-week change from baseline in depression score**, measured with the PROMIS 4-item depression scale from the PROMIS 29 profile at Visits 0 (baseline) and 2 (24 weeks of treatment)
- **24-week change from baseline in anxiety score**, measured with the PROMIS Emotional Distress-Anxiety scale (PROMIS-EDA 4a) at Visits 0 (baseline) and 2 (24 weeks of treatment)
- **24-week change from baseline in sleep disturbance,** measured with the PROMIS short form 6a at Visits 0 (baseline) and 2 (24 weeks of treatment)

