#### Objectives

The BEST trial was powered for the study's primary objective of estimating an algorithm to assign sequences of two cLBP treatments based on phenotypic markers and an individual patient's response to the initial treatment (i.e., a dynamic treatment regime (DTR)) that optimizes effectiveness, as characterized by the primary and secondary endpoints. In this outcome analysis, we will report the ITT-least squares adjusted mean of the 24-week outcomes of the BEST Trial and associated 95% confidence intervals. It is important to reiterate that the BEST trial was powered for biomarker discovery. This analysis describes the primary and secondary outcomes of the study.

[figure not shown]
In this analysis, we aim to:

- Report on BEST Trial study flow, baseline characteristics, and adverse events
- Estimate 24-week least squares means for study outcomes by Stage 1 treatment assignment.

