#### **Baseline Characteristics**

List of Baseline Characteristics to be summarized

The baseline characteristics analyzed are:

- Age
- Sex Assigned at Birth
- Gender Identity
- Ethnicity
- Race
- Highest Level of Education Completed
- Current Employment Status
- Current Relationship Status
- Number of People Living in Household
- Annual household income from all sources
- PEG score (0 to 10)
- Self-Reported low-back pain duration (months)
- Self-reported low-back pain duration (category)
- Low-back Pain Frequency in the Past 6 months
- Low-back Pain Specific Pain Intensity
- Ever had a low back operation?
- When was the last back operation?
- Any back operations involve a spinal fusion?
- Ever unemployed for 1 or more months due to low back pain
- Ever file or awarded worker's compensation claim related to back problem
- Involved in a lawsuit or legal claim related to back problem
- Ever applied for, or received, disability insurance for pain condition
- BMI
- Systolic Blood Pressure (mmHg)
- Diastolic Blood Pressure (mmHg)
- Heart Rate (bpm)
- Ever had Hip Replacement surgery?
- Ever had Knee Replacement surgery?
- Observed Gait
- Tobacco Use in Previous 12 Months
- Alcohol Use in Previous 12 Months
- Drug Use in Previous 12 Months
- Prescription Drug Used Not as Intended in Previous 12 Months
- Currently Taking Opioid Medication (daily)
- Previously diagnosed with COVID-19
- Long COVID
- COVID-19 Vaccine

- Fear avoidance beliefs about physical activity raw scoring scale 2
- GAD-2 Raw Score
- Keele STarT Back Screening Tool Risk
- Oswestry Disability Index Percentage
- Pain Catastrophizing Scale SF-6
- Pain Detect Questionnaire Raw Score
- PHQ-2 Raw Score
- HEAL Positive Outlook Raw Score
- PROMIS-Cognitive Function Abilities 2a Raw Score
- General Sensory Sensitivity Score External
- General Sensory Sensitivity Score Interoception
- General Sensory Sensitivity Score Total
- Self-reported Sleep Duration in the Past Month (hours)
- Symptom Severity Index
- Widespread Pain Raw Score
- Stomach Pain in the Past 4 Weeks
- Headaches in the Past 4 Weeks
- Radiating Pain to Buttock/Thigh, Past 2 Weeks
- Radiating Pain to Below Knee, Past 2 Weeks
- Social Determinants of Health: Transportation Needs
- Social Determinants of Health: Healthcare Needs
- Social Determinants of Health: Food Insecurity
- Social Determinants of Health: Food Money
- Social Determinants of Health: Utilities
- Social Determinants of Health: Stable Housing

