## **Analysis**

#### **Analysis Methods**

A linear mixed-effect model (LMM) was used to model the least squares mean of the primary and secondary outcomes at Visit 2 (Week 24) by the Stage 1 treatment assignment for all continuous outcomes. Random intercepts and a linear random slope for time were included to account for subject-level variability. The randomization and minimization algorithm variables are included as

fixed effects. Week indicators as fixed effects were included to model non-linear effects of time. An additional fixed effect was included for the number of treatments a participant was eligible for at the baseline visit. Estimation was conducted using REML and modern optimization approaches with the lme4 package in R. Least squares means were estimated for each Week 24 outcome, along with associated 95% confidence intervals, using the emmeans package in R. Due to the small number of participants on opioids in the BEST Trial sample, we only report counts of participants self-reporting opioid use at Week 24.

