#### **Outcome Definitions**

Outcome	Outcome Type	Specification	Specific	Calculation to	Analysis
Name	(primary/secondary)	of outcome	measurement	derive	Method
		and timing	and units	outcome	
Patient-	Primary	PEG Score	The PEG scale	Calculate the	LMM
Reported		measured at	is based on a	PEG Score by	
Pain		the Visit 2	participant	averaging the	
Intensity		(Week 24)	rating of their	responses	
and			pain in 3	from each of	
Interference			areas: pain	the 3 scales.	
Score			intensity, pain		
			interference		
			with		
			enjoyment of		
			life, and pain		
			interference		
			with general		
			activities. A		
			rating is given		
			ranging from -		
			10 (lowest) to		
			10 (highest)		
			on each of		
			these scales.		
			We use the		
			average of		
			these ratings,		
			with higher scores		
			indicating		
			increased		
			pain intensity		
			and		
			interference		
			at 24 Weeks		
			compared to		
			Baseline.		
Pain	Secondary	Pain	Ratings of the	Calculate the	LMM
Interference		Interference	consequences	raw score by	

		at Visit 2 (Week 24)	of pain on relevant aspects of one's life. This includes the extent to which the pain hinders engagement with social, cognitive, emotional, physical, and recreational activities. Results range from -34 to 34 (t-scores range from 41.6 to 75.6), with higher scores indicating increased pain interference at 24 Weeks compared to	summing all appropriate responses, then translate the raw score to the corresponding T-Score	
Physical Function	Secondary	Physical Function at Visit 2 (Week 24)	Baseline.  Measured by the PROMIS-PF Short Form 6b. The PROMIS-PF Short Form 6b is a series of 6 questions.  Results range from -37.1 to 37.1 (t-scores range from 21.6 to 58.7), with higher scores indicating increased physical functioning at 24 Weeks	Calculate the raw score by summing all appropriate responses, then translate the raw score to the corresponding T-Score	LMM

			compared to Baseline.		

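### The SAP derives its seven continuous outcomes as Week 24 levels but gives them change-from-baseline ranges, and it never names the protocol's 24-week change as an estimate

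*SAP*

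**What the plan says.** Protocol 4.1, repeated in sections 6 and 12.1: "The primary endpoint for the study is 24-week change from baseline in patient-reported pain intensity and interference", measured with the PEG. On scoring, section 12.1 states: "Response values for each item range from 0 to 10 and the average score across the three items will be used as the outcome value". Six of the seven secondary endpoints are also 24-week changes. The seventh, opioid use, is an incidence at Visit 2.

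The SAP's Outcome Definitions table describes the seven continuous outcomes in two ways within the same rows:

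- The timing column places each at Visit 2 (Week 24). The derivation column averages the three items (PEG), or sums items and converts to a T-score (PROMIS). Nothing is subtracted. The derivation cell for sleep duration is blank.
- The units column gives a range symmetric about zero and says that higher values mean an increase relative to baseline, for example "Results range from -34 to 34 (t-scores range from 41.6 to 75.6), with higher scores indicating increased pain interference at 24 Weeks compared to" baseline. For PEG, it assigns -10 to 10 to each item rating.

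Elsewhere the SAP speaks only of Week 24 values. Its aim is to "Estimate 24-week least squares means for study outcomes by Stage 1 treatment assignment", and Analysis Methods says "Least squares means were estimated for each Week 24 outcome, along with associated 95% confidence intervals". Its list of baseline characteristics has "PEG score (0 to 10" as the scale.

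**The concern.** A level and a change are different quantities, and the table describes both under one outcome name. The SAP plans no hypothesis tests, so its efficacy output is a set of arm-specific means with confidence intervals. For such means the definition decides the number: level and change differ by the arm's whole baseline mean. A PEG level read on a change scale can also reverse the apparent direction of effect. The protocol leaves the detail of the endpoint analyses to the SAP (13.4.2 and 13.4.3), so nothing else in the two documents settles which quantity is meant.

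**Working it through.** **Inputs.** T-score limits and stated symmetric ranges come from the SAP's Outcome Definitions table. PEG limits come from Protocol 12.1. For sleep duration, 0 to 24 hours is the natural limit of hours in a day.

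**Step 1: what the stated ranges are.** If a level lies between L and U, a change lies between -(U - L) and +(U - L). For pain interference this reproduces the SAP's figure: 75.6 - 41.6 = 34.0, stated as -34 to 34.

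**Step 2: could a Week 24 level lie in the stated range?** With stated range -R to R, the share of the level scale inside it is max(0, min(U, R) - max(L, -R)) / (U - L).

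| Outcome | Level scale L to U | U - L | Stated R | Share of level scale inside -R to R |
|---|---|---|---|---|
| PEG | 0 to 10 | 10 | 10 | 100% |
| Pain interference | 41.6 to 75.6 | 34.0 | 34 | 0% (41.6 > 34) |
| Physical function | 21.6 to 58.7 | 37.1 | 37.1 | 15.5/37.1 = 42% |
| Depression | 41.0 to 79.4 | 38.4 | 38.4 | 0% (41.0 > 38.4) |
| Anxiety | 40.3 to 81.6 | 41.3 | 41.3 | 1.0/41.3 = 2% |
| Sleep disturbance | 31.7 to 76.1 | 44.4 | 44.4 | 12.7/44.4 = 29% |
| Sleep duration (h) | 0 to 24 | 24 | 24 | 100% |

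All seven values of R equal U - L exactly. These are change-score ranges. Seven exact matches also rule out stray minus signs from text extraction.

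**Step 3: the PEG item range.** The range -10 to 10 is correct for a change in the PEG score. It is wrong for an item rating, which runs from 0 to 10.

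**Step 4: level against change for PEG.** Change = Week 24 level - baseline. The mean PEG at Week 0 is not in the documents; the entry rule of PEG 4 or higher applied before run-in, not at Visit 0. Taking means of 5, 6 and 7 as assumptions, a Week 24 level of 4 gives:

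- 4 - 5 = -1
- 4 - 6 = -2
- 4 - 7 = -3

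Read on the units column's scale, the value 4 is a worsening of 4 points. The misreading equals the baseline mean: 4 - (-1) = 5 up to 4 - (-3) = 7 points.

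**The case against.** The strongest reply is that little depends on this. The SAP's section on multiplicity says that the trial's primary estimand, the value of the estimated optimal treatment regime, lies outside this analysis. Between randomised arms, level and change contrasts have the same expectation, so no comparison of arms is biased. The appendices have no shell for an outcome results table, so a mislabelled table is a possibility and not something in the plan. The PROMIS rows print the T-score limits beside the symmetric range, so a reader would probably recognise a T-score level. All of this stands and limits the harm. It does not remove the contradiction: arm-specific means are the only efficacy estimates this SAP names, and the PEG row has no second range to alert the reader.

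A reader might infer three stronger points that the documents do not support.

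- *That the result is neither the protocol endpoint nor readable on its scale.* If change was intended, it is the protocol endpoint and the ranges are right for the scores; only the PEG item wording and the missing subtraction are wrong. The table is ambiguous between two readings.
- *That every outcome is affected.* Opioid use is a Week 24 count with no change scale, and it agrees with the protocol's incidence definition.
- *That the mixed model cannot be identified.* The SAP says: "Random intercepts and a linear random slope for time were included to account for subject-level variability". Two random-effect variances, one covariance and one residual variance make 4 parameters, against 3 distinct elements of a 2 x 2 covariance matrix. That count applies only if change is modelled at Weeks 12 and 24 alone, which the SAP does not say. The protocol's schedule of activities also has PROMIS and sleep duration at Weeks 0 and 36; three modelled times give 6 elements. PEG is collected at Weeks 6 and 18 as well. The SAP also keeps every randomised participant however few later observations there are, which sits more naturally with Week 0 in the outcome vector.

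**Conclusion.** The table is wrong as written for seven of the eight outcomes. Two findings need no assumption: the PEG item range contradicts both the protocol and the SAP's own baseline list, and two PROMIS outcomes have stated ranges that contain no attainable Week 24 T-score. It also follows from the text that the protocol's change endpoint is nowhere named as an estimate. The aim, timing and analysis method point to a level, as do the derivations that are given; only the units column points to change.

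The gap between the two readings is the full baseline mean of each scale. The illustration of 5 to 7 PEG points rests on assumed baseline means and says nothing about the size on the other six scales. Primary here means the label in the SAP's outcome table, not the trial's primary estimand.

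**What to change.** 1. Correct the PEG item rating to 0 to 10.
2. State the modelled outcome and the visits in the outcome vector. One suitable choice is the score on its native scale at every modelled visit, including Week 0. Fill in the blank derivation for sleep duration.
3. For each arm, report the Week 24 least squares mean on its native scale, and the model-based Week 24 minus Week 0 change with a 95% confidence interval. For that change to vary by arm the model needs arm-by-week terms; Analysis Methods does not list them, so they should be stated.
4. Attach the symmetric ranges and the comparison with baseline to the change estimate only. Give the level its own range.

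The cost is SAP wording and one extra contrast per outcome. No new data are needed.

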#### **Missing Data**

We assume the data are missing at random. We include all subjects randomized at baseline in the analysis, regardless of the number of future observations. There is no missingness in model covariates because they were required for randomization at the baseline visit.

### **Additional Analyses**

Additional reporting is included in this submission for adverse events (Appendix 3)

# **Table 1.0. BEST Trial Recruitment Flow Diagram**

# All Randomized Participants at Baseline

Arm/Group Title	Acceptance and Commitment Therapy (ACT) Alone	ACT Plus Duloxetine, Moderate Treatment Response	ACT Plus Evidence Based Exercise and Manual Therapy (EBEM), Moderate Stage 1 Treatment Response	ACT Plus Enhanced Self-Care Therapy (ESC), Moderate Stage 1 Treatment Response	ACT Plus Duloxetine, Low Stage 1 Treatment Response	ACT Plus Evidence Based Exercise and Manual Therapy (EBEM), Low Stage 1 Treatment Response	ACT Plus Enhanced Self-Care Therapy (ESC), Low Stage 1 Treatment Response
Arm/Group Description	This arm included both participants who had a strong response to ACT in Stage 1 and participants who were not assessed for response at the end of Stage 1. In Stage 1, participants randomized to ACT took part in 12 therapy sessions over the course of 12 weeks. Each participant was scheduled for a combination of 4 remote face-to-face visits and 8 therapist-supported online sessions, which included a self-directed module combined with personalized provider coaching delivered via an online messaging system. In Stage 2, strong responders were encouraged to continue to practice ACT skills at home without therapist supervision and were given access to an additional 11 ACT audio modules.	This arm included participants who had a moderate response to ACT in Stage 1 and started Duloxetine in Stage 2 while continuing ACT treatment.	This arm included participants who had a moderate response to ACT in Stage 1 and started EBEM treatment in Stage 2 while continuing ACT.	This arm included participants who had a moderate response to ACT in Stage 1 and started ESC treatment in Stage 2 while continuing ACT.	This arm included participants who had a low response to ACT in Stage 1 and started Duloxetine treatment in Stage 2 while continuing ACT.	This arm included participants who had a low response to ACT in Stage 1 and started EBEM treatment in Stage 2 while continuing ACT.	This arm included participants who had a low response to ACT in Stage 1 and started ESC treatment in Stage 2 while continuing ACT.
Stage 1 Intervention (Weeks 0-12)							
Started							
Completed							
Not Completed							
Reason Not Completed							
Stage 2 Screening (Week 12 Pre- Randomization)							
Started							
Completed							
Not Completed							
Reason Not Completed							
Stage 2 Intervention (Weeks 12-24)							
Started							
Completed							
Not Completed							
Reason Not Completed							

Arm/Group Title	ACT Followed by Duloxetine, Low Stage 1 Treatment Response	ACT Followed by Evidence Based Exercise and Manual Therapy (EBEM), Low Stage 1 Treatment Response	ACT Followed by Enhanced Self-Care Therapy (ESC), Low Stage 1 Treatment Response	ACT Followed by Duloxetine, Poor Stage 1 Treatment Response	ACT Followed by Evidence Based Exercise and Manual Therapy (EBEM), Poor Stage 1 Treatment Response	ACT Followed by Enhanced Self-Care Therapy (ESC), Poor Stage 1 Treatment Response	Duloxetine Alone
Arm/Group Description	This arm included participants who had a low response to ACT in Stage 1 and started Duloxetine treatment in Stage 2. ACT treatment was discontinued.	This arm included participants who had a low response to ACT in Stage 1 and started EBEM treatment in Stage 2. ACT treatment was discontinued.	This arm included participants who had a low response to ACT in Stage 1 and started ESC treatment in Stage 2. ACT treatment was discontinued.	This arm included participants who had a poor response to ACT in Stage 1 and started Duloxetine treatment in Stage 2. ACT treatment was discontinued.	This arm included participants who had a poor response to ACT in Stage 1 and started EBEM treatment in Stage 2. ACT treatment was discontinued.	This arm included participants who had a poor response to ACT in Stage 1 and started ESC treatment in Stage 2. ACT treatment was discontinued.	This arm included both participants who had a strong response to Duloxetine in Stage 1 and participants who were not assessed for response at the end of Stage 1.
Stage 1 Intervention (Weeks 0-12)							
Started							
Completed							
Not Completed							
Reason Not Completed							
Stage 2 Screening (Week 12 Pre- Randomization)							
Started							
Completed							
Not Completed							
Reason Not Completed							
Stage 2 Intervention (Weeks 12-24)							
Started							
Completed							
Not Completed							
Reason Not Completed							

Arm/Group Title	Duloxetine Plus Acceptance and Commitment Therapy (ACT), Moderate Stage 1 Treatment Response	Duloxetine Plus Evidence Based Exercise and Manual Therapy (EBEM), Moderate Stage 1 Treatment Response	Duloxetine Plus Enhanced Self-Care Therapy (ESC), Moderate Stage 1 Treatment Response	Duloxetine Plus Acceptance and Commitment Therapy (ACT), Low Stage 1 Treatment Response	Duloxetine Plus Evidence Based Exercise and Manual Therapy (EBEM), Low Stage 1 Treatment Response	Duloxetine Plus Enhanced Self-Care Therapy (ESC), Low Stage 1 Treatment Response	Duloxetine Followed by Acceptance and Commitment Therapy (ACT), Low Stage 1 Treatment Response
Arm/Group Description	This arm included participants who had a moderate response to Duloxetine in Stage 1 and started ACT treatment in Stage 2 while continuing Duloxetine.	This arm included participants who had a moderate response to Duloxetine in Stage 1 and started EBEM treatment in Stage 2 while continuing Duloxetine.	This arm included participants who had a moderate response to Duloxetine in Stage 1 and started ESC treatment in Stage 2 while continuing Duloxetine.	This arm included participants who had a low response to Duloxetine in Stage 1 and started ACT treatment in Stage 2 while continuing Duloxetine.	This arm included participants who had a low response to Duloxetine in Stage 1 and started EBEM treatment in Stage 2 while continuing Duloxetine.	This arm included participants who had a low response to Duloxetine in Stage 1 and started ESC treatment in Stage 2 while continuing Duloxetine.	This arm included participants who had a low response to Duloxetine in Stage 1 and started ACT treatment in Stage 2. Duloxetine treatment was discontinued.
Stage 1 Intervention (Weeks 0-12)							
Started							
Completed							
Not Completed							
Reason Not Completed							
Stage 2 Screening (Week 12 Pre- Randomization)							
Started							
Completed							
Not Completed							
Reason Not Completed							
Stage 2 Intervention (Weeks 12-24)							
Started							
Completed							
Not Completed							
Reason Not Completed							

Arm/Group Title	Duloxetine Followed by Evidence Based Exercise and Manual Therapy (EBEM), Low Stage 1 Treatment Response	Duloxetine Followed by Enhanced Self-Care Therapy (ESC), Low Stage 1 Treatment Response	Duloxetine Followed by Acceptance and Commitment Therapy (ACT), Poor Stage 1 Treatment Response	Duloxetine Followed by Evidence Based Exercise and Manual Therapy (EBEM), Poor Stage 1 Treatment Response	Duloxetine Followed by Enhanced Self-Care Therapy (ESC), Poor Stage 1 Treatment Response	Evidence Based Exercise and Manual Therapy (EBEM) Alone	EBEM Plus Duloxetine, Moderate Stage 1 Treatment Response
Arm/Group Description	This arm included participants who had a low response to Duloxetine in Stage 1 and started EBEM treatment in Stage 2. Duloxetine treatment was discontinued.	This arm included participants who had a low response to Duloxetine in Stage 1 and started ESC treatment in Stage 2. Duloxetine treatment was discontinued.	This arm included participants who had a poor response to Duloxetine in Stage 1 and started ACT treatment in Stage 2. Duloxetine treatment was discontinued.	This arm included participants who had a poor response to Duloxetine in Stage 1 and started EBEM treatment in Stage 2. Duloxetine treatment was discontinued.	This arm included participants who had a poor response to Duloxetine in Stage 1 and started ESC treatment in Stage 2. Duloxetine treatment was discontinued.	This arm included both participants who had a strong response to EBEM in Stage 1 and participants who were not assessed for response at the end of Stage 1.	This arm included participants who had a moderate response to EBEM in Stage 1 and started Duloxetine treatment in Stage 2 while continuing EBEM.
Stage 1 Intervention (Weeks 0-12)							
Started							
Completed							
Not Completed							
Reason Not Completed							
Stage 2 Screening (Week 12 Pre- Randomization)							
Started							
Completed							
Not Completed							
Reason Not Completed							
Stage 2 Intervention (Weeks 12-24)							
Started							
Completed							
Not Completed							
Reason Not Completed							

Arm/Group Title	EBEM Plus Acceptance and Commitment Therapy (ACT), Moderate Stage 1 Treatment Response	EBEM Plus Enhanced Self-Care Therapy (ESC), Moderate Stage 1 Treatment Response	EBEM Plus Duloxetine, Low Stage 1 Treatment Response	EBEM Plus Acceptance and Commitment Therapy (ACT), Low Stage 1 Treatment Response	EBEM Plus Enhanced Self-Care Therapy (ESC), Low Stage 1 Treatment Response	EBEM Followed by Duloxetine, Low Stage 1 Treatment Response	EBEM Followed by Acceptance and Commitment Therapy (ACT), Low Stage 1 Treatment Response
Arm/Group Description	This arm included participants who had a moderate response to EBEM in Stage 1 and started ACT treatment in Stage 2 while continuing EBEM.	This arm included participants who had a moderate response to EBEM in Stage 1 and started ESC treatment in Stage 2 while continuing EBEM.	This arm included participants who had a low response to EBEM in Stage 1 and started Duloxetine treatment in Stage 2 while continuing EBEM.	This arm included participants who had a low response to EBEM in Stage 1 and started ACT treatment in Stage 2 while continuing EBEM.	This arm included participants who had a low response to EBEM in Stage 1 and started ESC treatment in Stage 2 while continuing EBEM.	This arm included participants who had a low response to EBEM in Stage 1 and started Duloxetine treatment in Stage 2. EBEM treatment was discontinued.	This arm included participants who had a low response to EBEM in Stage 1 and started ACT treatment in Stage 2. EBEM treatment was discontinued.
Stage 1 Intervention (Weeks 0-12)							
Started							
Completed							
Not Completed							
Reason Not Completed							
Stage 2 Screening (Week 12 Pre- Randomization)							
Started							
Completed							
Not Completed							
Reason Not Completed							
Stage 2 Intervention (Weeks 12-24)							
Started							
Completed							
Not Completed							
Reason Not Completed							

Arm/Group Title	EBEM Followed by Enhanced Self-Care Therapy (ESC), Low Stage 1 Treatment Response	EBEM Followed by Duloxetine, Poor Stage 1 Treatment Response	EBEM Followed by Acceptance and Commitment Therapy (ACT), Poor Stage 1 Treatment Response	EBEM Followed by Enhanced Self-Care Therapy (ESC), Poor Stage 1 Treatment Response	Enhanced Self-Care Therapy (ESC) Alone	ESC Plus Duloxetine, Moderate to Low Stage 1 Treatment Response	ESC Plus Acceptance and Commitment Therapy (ACT), Moderate to Low Stage 1 Treatment Response	ESC Plus Evidence Based Exercise and Manual Therapy (EBEM), Moderate to Low Stage 1 Treatment Response
Arm/Group Description	This arm included participants who had a low response to ESC in Stage 1 and started Duloxetine treatment in Stage 2. EBEM treatment was discontinued.	This arm included participants who had a poor response to EBEM in Stage 1 and started Duloxetine treatment in Stage 2. EBEM treatment was discontinued.	This arm included participants who had a poor response to EBEM in Stage 1 and started ACT treatment in Stage 2. EBEM treatment was discontinued.	This arm included participants who had a poor response to EBEM in Stage 1 and started ESC treatment in Stage 2. EBEM treatment was discontinued.	This arm included both participants who had a strong response to ESC in Stage 1 and participants who were not assessed for response at the end of Stage 1.	This arm included participants who had a moderate to poor response to ESC in Stage 1 and started Duloxetine treatment in Stage 2. ESC treatment was discontinued.	This arm included participants who had a moderate to poor response to ESC in Stage 1 and started ACT treatment in Stage 2. ESC treatment was discontinued.	This arm included participants who had a moderate to poor response to ESC in Stage 1 and started EBEM treatment in Stage 2. ESC treatment was discontinued.
Stage 1 Intervention (Weeks 0-12)								
Started								
Completed								
Not Completed								
Reason Not Completed								
Stage 2 Screening (Week 12 Pre- Randomization)								
Started								
Completed								
Not Completed								
Reason Not Completed								
Stage 2 Intervention (Weeks 12-24)								
Started								
Completed								
Not Completed								
Reason Not Completed								

Table 1: Tabular Characteristics of Randomized Population

	ACT	Duloxetine	EBEM	ESC	Total
Variable 	(N=203)	(N=198)	(N=199)	(N=205)	(N=805)
Age					
Age Group					
< 18 years					
18-65 years					
>65 years					
Sex Assigned at Birth, n(%) 					
Female					
Male					
Missing					
Gender Identity, n(%) Female					
Male					
Non-Binary					
Unknown					
Missing					
Ethnicity, n(%)					
Hispanic or Latino					
Not Hispanic or Latino					
Unknown/Not Reported					
Missing					
Race, n(%)					
White					
Black, African American, or Black Multiracial					
Asian or Asian Multiracial					
Indigenous or Indigenous Multiracial					
Unknown or Not Reported					
Missing					
Highest Level of Education Completed, n(%)					
Did not complete Secondary School or High School					
High School or Secondary School Degree Complete					

Associate's or			
Technical Degree			
Complete			
College or			
Baccalaureate			
Degree Complete			
Doctoral or			
Postgraduate			
Education			
Missing			
Current			
Employment Status,			
n(%)			
Full-time			
employment			
Not employed 			
Part-time			
employment			
Missing			
Current			
Relationship Status,			
n(%)			
Married			
Never married			
Domestic Partner			
Widowed			
Divorced or			
Separated			
Missing			
Number of People			
Living in Household,			
n(%)			
1			
2			
3			
4			
5			
6			
7			
8			
Missing			
Annual household			
income from all			
sources, n(%)			
Less than			
\$10,000	 	 	
\$10,000 to	 	 	
\$24,999			
\$25,000 to			
\$34,999			

	•	•	
\$35,000 to			
\$49,999			
\$50,000 to \$74,999			
\$75,000 to \$99,999			
\$100,000 to \$149,999			
\$150,000 to			
\$199,999			
\$200,000 or more			
Prefer not to answer			
Missing			
PEG score (0 to 10)			
PEG score,			
median			
(range)			
Self-reported low- back pain duration			
(months)			
Self-reported low-			
back pain duration, n(%)			
< 1 year			
1-5 years			
> 5 years			
Missing			
Low Back Pain			
Frequency in the			
Past 6 months,			
n(%) Every day or			
nearly every day			
At least half the days			
Low Back Pain			
Specific Pain Intensity, (0 to 10)			
Low Back Pain SPI,			
median (range)			
Ever had low back			
operation, n(%)			
No			
Yes, at least one			
Missing	 	 	
When was last back operation, n(%)4		 	
Less than 6			
months ago	 	 	
More than 6	 	 	
months ago but			
less than 1 year			
ago			

D	1		-
Between 1 and 2 years ago			
More than 2 years ago			
Any back operations involve a spinal			
fusion, n(%)4 No			
Yes			
Not Sure			
Ever unemployed for 1 or more months due to low back pain, n(%)			
No			
Yes			
Does not apply			
Missing		 	
Ever filed or awarded worker's compensation claim related to back problem, n(%)			
No			
Yes			
Does not apply			
Missing			
Involved in a lawsuit or legal claim related to back problem, n(%)			
Yes			
Not sure			
Missing			
Ever applied for, or received, disability insurance for pain condition, n(%)			
Yes			
Missing			
ВМІ			
Systolic Blood			
Pressure (mmHg)			
Diastolic Blood Pressure (mmHg)			
Heart Rate (bpm)			
` ` `	1		

	,	1	
Ever Hip Replacement			
Surgery Yes			
No			
Missing			
Ever Knee Replacement			
Surgery			
Yes			
No			
Missing			
Observed Gait			
Normal			
Antalgic			
Missing			
Tobacco Use in Previous 12 Months			
Daily or Almost			
Daily Less Than Daily			
Never			
Missing			
Alcohol Use in			
Previous 12 Months			
At Least Weekly			
Monthly			
Less Than			
Monthly			
Never			
Missing			
Drug Use in			
Previous 12 Months Daily or Almost			
Daily of Affilost Daily			
Between Monthly			
to Weekly Less Than			
Monthly			
Never			
Missing			
Prescription Drug			
Used Not as			
Intended in Previous 12 Months			
At Least Once			
Never			
Missing			

а .1 1.			1
Currently Taking Opioid Medication			
(daily), n(%)			
Yes			
No			
Not sure			
Previously Diagnosed with			
COVID-19			
Yes			
No			
Not Sure			
Prefer not to			
Answer			
Missing			
Long COVID			
Yes			
No			
Not Sure			
Prefer not to			
Answer			
No self-reported COVID-19			
Diagnosis			
COVID-19 Vaccine			
Yes			
No			
Not Sure			
Prefer Not to			
Answer			
Fear-avoidance beliefs about			
physical activity raw			
scoring scale 2			
GAD-2 Raw Score			
Keele STarT Back Screening Tool Risk,			
n(%)			
Low Risk			
Medium Risk			
High Risk			
Missing			
Oswestry Disability			
Index Percentage			
ODI Percentage,			
median (range) Pain			
Catastrophizing Scale SF-6			

	1		
PainDetect Questionnaire Raw			
Score			
Nociceptive Pain			
Possible			
Neuropathic Pain			
Neuropathic pain			
Missing			
PHQ-2 Raw Score			
HEAL Positive			
Outlook Raw Score			
PROMIS-Cognitive Function - Abilities			
2a Raw Score			
General Sensory			
Sensitivity Score -			
External			
General Sensory Sensitivity Score -			
Interoception			
General Sensory			
Sensitivity Score -			
Total			
Self-reported Sleep			
Duration in the Past Month (hours)			
Symptom Severity			
Index			
Widespread Pain			
Raw Score			
Stomach Pain in the Past 4 Weeks			
Not bothered at			
all			
Bothered a little			
Bothered a lot			
Missing			
Headaches in the Past 4 Weeks			
Not bothered at all			
Bothered a little			
Bothered a lot			
Missing			
Radiating Pain to Buttock/Thigh, Past 2 Weeks			
Yes			
No			
Not Sure			
Missing			 

	1		
Radiating Pain to Below Knee, Past 2 Weeks			
Yes			
No			
Not Sure			
Missing			
Social Determinants of Health: Transportation Needs			
Yes			
No			
Missing			
Social Determinants of Health:			
Healthcare Needs Yes			
No			
Missing			
Social Determinants of Health: Food Insecurity			
Often True			
Sometimes True			
Never True			
Missing			
Social Determinants of Health: Food Money			
Often True			
Sometimes True			
Never True			
Missing			
Social Determinants of Health: Utilities			
Yes			
No			
Missing			
Social Determinants of Health: Stable Housing			
Yes		 	
No			
Missing			
Social Determinants of Health: Emotional Support			

Yes			
No			
Missing			
Social Determinants of Health: Number of Close Friends			
0			
1-2			
3-5			
6-10			
More than 10			
Missing			
Perceived Discrimination: Race/Ethnicity			
Never			
Rarely			
Sometimes			
Often to Almost Always			
Not sure			
Missing			
Perceived Discrimination: Orientation/Gender Identity			
Never			
Rarely			
Sometimes			
Often to Almost Always Not sure			
Missing			

<sup>1Discrete variable rows display count and percent, N (%). Continuous variable rows display mean and standard deviation, XX.X (YY.Y). Sex assigned at birth is defined as the most commonly reported identity collected from a participant across all visits.

<sup>3Counts retired, unemployed, and other participants who are not currently in the labor force.

Counts only include respondents who have answered either 'Yes, one operation' or 'Yes, more than one operation' when asked about prior low-back

operations.

5Participants who self-reported male sex at birth were asked about the frequency of >4 alcoholic drinks, while participants who self-reported female sex at birth were asked about the frequency of >3 alcoholic drinks.

